The study is designed as a pilot cluster randomized quality improvement trial. For each patient, a target clinician will be identified, defined as either a cardiologist at Michigan Medicine, if the patient has seen one in the past year, or else the clinician of record on file with the anticoagulation service. For each patient, assignment to one of two clinician-level QI strategies will be done at the cluster level according to the identity of the target clinician. Each clinician (cluster) will be randomized 1:1 to receive either clinician notification (consisting of a notification message sent in the electronic health record) or clinician notification + nurse facilitation (consisting of a similar notification, but which additionally includes provision of clinically relevant information identified on chart review, along with other steps to facilitate appropriate care). Separately, patients will be individually randomized to receive an activation guide that provides patient education and encouragement to discuss medication optimization with their clinicians, or to usual care. Following delivery of the QI strategies, patients, clinicians, and anticoagulation staff will be invited to participate in semi-structured interviews about their experiences with and perceptions of the QI strategies.

Group 1: Primary Objective: To explore the feasibility of patient participation in a one-time assessment of medication use following delivery of the QI strategies.

Group 1: Secondary Objectives: To explore the feasibility of delivering QI strategy components to clinicians and patients as intended.

Group 2: Primary Exploratory Objective: To explore the feasibility and appropriateness of the QI strategies from the perspective of primary care clinicians to inform a future clinic-wide trial.

Endpoints*:

Group 1: Primary Endpoint: The proportion of randomized patients who complete a brief phone assessment (patient assessment #1) at week 5.

Group 1: Secondary Endpoints: The proportion of patients and clinicians who received the QI strategies to which they were randomized.

Group 1: Exploratory Endpoints: Multiple additional quantitative endpoints will be evaluated, as documented in the section 4 of the protocol.

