2 INTRODUCTION

2.1 Study Rationale & Background

Increasing numbers of patients in the United States are prescribed oral anticoagulants to treat or prevent a range of thromboembolic conditions ¹. The main risk with anticoagulants is major bleeding, most commonly from the gastrointestinal tract ^{2,3}. Many patients prescribed anticoagulants are co-prescribed an antiplatelet drug (aspirin or a thienopyridine), and these patients are at particularly high risk for major bleeding. In an observational study of patients prescribed warfarin, use of an antiplatelet drug increased the risk of major bleeding (5.7% vs. 3.3%), emergency department visits for bleeding (13.3% vs. 9.8%), and hospitalizations for bleeding (8.1% vs. 4.1%), but did not reduce the rate of thrombosis ⁴.

Medication optimization can substantially reduce bleeding risk for patients prescribed combination antithrombotic therapy (CAT). One evidence-based practice is to discontinue antiplatelet therapy in patients for whom it is inappropriate. Based on recent clinical trial data, the indications for CAT are increasingly narrow, and most patients prescribed anticoagulants should only use antiplatelet drugs for a limited time after acute coronary syndrome, coronary stenting, or other vascular procedures ⁵. A second evidence-based practice is the use of a proton pump inhibitor (PPI gastroprotection) for patients in whom CAT is truly indicated, a strategy recommended by professional guidelines ^{5,6}. A meta-analysis showed PPIs reduce the risk of UGIB by up to 79% in patients using aspirin or non-steroidal anti-inflammatory drugs ⁷. Both of these evidence-based practices are underused ⁸. In an observational study of six anticoagulation clinics, 45% of patients prescribed warfarin were co-prescribed an antiplatelet drug. Of these, 44% had no identifiable indication for antiplatelet therapy, and 36% were appropriately prescribed CAT but without a PPI ⁸.

There are multiple barriers to use of these evidence-based practices. Clinicians may lack knowledge of appropriate use of medication optimization strategies, have inadequate time or prioritization, or lack “ownership,” since many patients are co-managed by a PCP and a subspecialist (typically a cardiologist) ⁹. In many cases, a clinician may be prepared to assess

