
To explore the feasibility of prompting patient-clinician communication about medication optimization
	
The number of days after delivery of the clinician-facing QI strategy at which the patient and the target clinician (or their healthcare team) had communication (either by phone, in person visit, or portal message) about medication optimization, based on chart review. This will be calculated overall and separately for each QI strategy.
 
The proportion of patients who had a communication about medication optimization with their clinicians based on patient recall at week 5 (patient assessment #1) and at week 9-12 (patient assessment #3). This will be calculated overall and separately for each QI strategy.
 
For patients who had a communication with their clinician about medication optimization, the proportion in whom initial contact was made by the clinician vs. by the patient, according to chart review. This will be calculated overall and separately for each of the QI strategies. This will be assessed based on week 5 call.
 
For patients who had a communication with their clinician about medication optimization, the proportion in whom initial contact was made by the clinician vs. by the patient, according to patient recall. This will be calculated overall separately for each QI strategy.
 
For patients who contacted a clinician about medication optimization, the specialty of the clinician and whether the clinician who was sent the clinician notification was the target clinician. This will be determined separately based on chart review and patient recall.
 
For patients who had communication with their clinician documented in the electronic health record, whether this occurred by phone, portal, or in-person/telehealth visit based on chart review.

To explore process measures associated with clinician notification
	
For clinicians randomized to clinician notification:
 
Number of days taken for clinicians to send a response message to anticoagulation staff after first receiving the clinician QI strategy.
 
Proportion of clinicians who documented their plan-of-care for the patient in the response message to the anticoagulation staff.
 
The number of clinicians who appropriately documented changes in antiplatelet drugs or PPI in the EHR medication list.

OBJECTIVES	ENDPOINTS

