7 STUDY QUALITY IMPROVEMENT STRATEGIES

7.1 Study Implementation Strategy Administration

7.1.1 Quality Improvement Strategy Descriptions

All of the implementation strategies have been documented into clinical protocols approved by the anticoagulation clinic to address upper GI bleeding risk. All study QI strategies will be delivered by anticoagulation clinic staff as part of routine care.

Two clinician-facing implementation strategies will be evaluated.

1. **Clinician Notification:** An anticoagulation clinic nurse sends a templated message to the patient's target clinician that points out the patient's high risk for upper GI bleeding, summarizes guidelines on appropriate antiplatelet drug use and PPI gastroprotection, and recommends that the clinician consider either discontinuing the patient's antiplatelet drug or initiating a PPI for gastroprotection.
2. **Clinician Notification + Nurse facilitation:** An anticoagulation clinic nurse sends a templated message to the target clinician, similar to the clinician notification strategy. However, the message also includes clinical details about the patient's indication for antiplatelet therapy, ascertained by the nurse during chart review, and is intended to streamline decision-making by the clinician. In addition, the nurse will pend orders for medication changes if given instructions by the clinician and will communicate any recommendations to the patient on the clinician's behalf.

In addition, two patient-facing implementation strategies will be evaluated:

1. **Patient Activation:** A written guide to educate patients about their risk for bleeding and encouraging patients to talk with their clinician about medication changes to reduce their bleeding risk. This will be sent to patients through their preferred mode of communication (mail or patient portal). All patients will only be sent the guide once.
2. **Usual care:** With usual care, the anticoagulation clinic will not send the patient activation guide or other project-specific materials to the patient.

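### One exploratory communication item is yes by definition, and the only chart-based timing endpoint leaves out talks with any clinician other than the target

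*Combined protocol and SAP*

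**What the plan says.** The Synopsis (1.1) gives each patient a single addressee for the clinician-level strategy: "a target clinician will be identified, defined as either a cardiologist at Michigan Medicine, if the patient has seen one in the past year", and otherwise the clinician of record with the anticoagulation service. Section 7.1.1 directs both clinician strategies to that person. In the notification arm the nurse "sends a templated message to the patient's target clinician that points out" the bleeding risk. In the facilitation arm the nurse "sends a templated message to the target clinician, similar to the clinician notification strategy".

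The patient-level strategy is broader. The Synopsis describes the guide as giving "encouragement to discuss medication optimization with their clinicians", and 7.1.1 describes it as "encouraging patients to talk with their clinician about medication changes to reduce their bleeding risk". Neither description steers the patient to the target clinician.

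Section 4.1 then lists exploratory endpoints on patient-clinician communication. Two matter here:

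- For patients who contacted a clinician about medication optimization, the specialty of that clinician and "whether the clinician who was sent the clinician notification was the target clinician", taken separately from chart review and patient recall.
- The number of days from delivery of the clinician-facing strategy until "the patient and the target clinician (or their healthcare team) had communication" about medication optimization, from chart review, reported overall and for each QI strategy.

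Section 4.2 repeats both for Group 2, from chart review only.

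**The concern.** The first item appears to ask about the wrong clinician. It concerns who received the message, which the protocol fixes in advance. What varies, and what a pilot pairing two strategies would want to know, is whom the patient went to.

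The second endpoint reports results for the guide under a definition built around the recipient of the clinician message. Section 2.1 describes unclear ownership as a barrier, "since many patients are co-managed by a PCP and a subspecialist". When the target is a cardiologist, a guide patient who raises the matter with the PCP contributes no event to the timing endpoint, even if the talk is fully documented.

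At stake is planning information for the later trial: whether activated patients reach the clinician who was alerted, and how soon the guide leads to a conversation with anyone.

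**Working it through.** No arithmetic applies, and the plan states no figure on this point. The check sets the definitions side by side.

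**1. The notified-clinician item**

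- There is one target clinician per patient (1.1), and both strategies are messages to that target (7.1.1). Under correct delivery, the notified clinician is the target.
- A no could arise only from a misdirected message. That is a question of delivery, for which 4.1 already has separate endpoints.
- The item sits under patient-clinician communication, is restricted to patients who contacted a clinician, is paired with that clinician's specialty, and has patient recall as one source. The protocol describes no step that tells patients who was messaged, although a patient in the facilitation arm might infer it. All of this fits a question about the clinician contacted, which is probably what was meant.
- For Group 2, section 6.1.2 calls the eight primary care clinicians the target clinicians, so the answer is again yes. If the Synopsis definition were applied to a Group 2 patient who had seen a cardiologist in the past year, a no could appear. It would reflect the definition and not what the patient did.

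**2. The days-to-communication endpoint**

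- Counted: chart-documented communication with the target clinician or that clinician's healthcare team.
- Not counted: communication with any other clinician.
- Reported for: each QI strategy, which includes the guide. Guide and clinician message are started together (1.3), so the same clock could serve both.

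**3. Where a documented talk with a non-target clinician can still appear**

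| Chart-based exploratory endpoint | Limited to the target? |
|---|---|
| Days to communication (4.1, 4.2) | Yes, plus the target's team |
| Specialty of the clinician the patient contacted | No, any clinician |
| Documented recommendation to stop antiplatelet therapy or start a PPI | No, any of the patient's Michigan Medicine clinicians |
| Who initiated contact | Probably not; the clinician is not further defined |
| Mode of contact | Probably not; same undefined wording |

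In Group 1 the recall-based proportion with any communication also covers the patient's clinicians generally. No chart-based proportion with any communication is listed, and no row classifies the contacted clinician as target or non-target. Specialty is only a proxy: a different cardiologist would look the same as a cardiologist target.

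**The case against.** The strongest defence concerns the timing endpoint. Its clock starts when the clinician-facing strategy is delivered, and that strategy goes to the target. Read as a measure of response to that strategy, restriction to the target is sensible. This stands, and it is why the target-only version should stay. It does not cover reporting the same endpoint for the guide.

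Three stronger readings are tempting, and the documents do not support them:

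- A reader might infer that talks with other clinicians are lost from the chart-based results altogether. They are lost from one endpoint. The specialty and recommendation items admit them, and the initiator and mode items probably do.
- A reader might infer that the pilot has no means of learning where activated patients go. Specialty is collected from chart and recall, each patient's target is known beforehand, and patient assessment #2 (9.2.2) asks guide recipients about discussions with their clinicians. Together these answer part of the question, though not explicitly and not by the identity of the clinician.
- A reader might want to put a percentage on how far the guide's effect on communication is understated. The endpoint is a number of days, not a proportion, and the documents give neither a communication rate nor a share of talks with non-target clinicians.

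Nor is it a contradiction that the chart and recall measures differ in scope. One is time to contact with the target or team; the other is the proportion recalling any contact. They should simply not be compared as if they measured the same thing.

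The example of a PCP talk missed because the target is a cardiologist is a Group 1 example, and there six of the 12 clinicians are non-cardiologist clinicians of record (6.4.1). In Group 2 the target is the primary care clinician, so a talk with that clinician counts and the omitted talks would be those with others.

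**Conclusion.** The point holds as two wording defects in exploratory endpoints. The notified-clinician item is constant whenever messages go out per protocol, and nothing else in 4.1 or 4.2 records whether the clinician contacted was the target. The only chart-based timing measure omits documented talks with non-target clinicians although it is also reported for the guide.

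No numerical magnitude is claimed. The conclusion assumes that the target is the person defined in 1.1 (6.1.2 for Group 2) and that messages are sent as 7.1.1 describes. Section 11.7 plans mainly descriptive analysis of these endpoints, and the primary and secondary endpoints do not depend on them. This is a low-severity correction worth making because it is cheap.

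**What to change.** In both 4.1 and 4.2:

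1. Replace the notified-clinician item with: whether the clinician contacted was the target clinician.
2. Keep the days-to-communication endpoint for the target clinician or team as it stands.
3. Add a companion endpoint: days to the first documented communication about medication optimization with any Michigan Medicine clinician, split by target versus non-target.

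It would also help to state whether the clinician in the initiator and mode items means the target or any clinician.

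The cost is endpoint wording and slightly more chart abstraction. Chart review is already planned and already captures the specialty of the clinician contacted. Contacts with clinicians outside Michigan Medicine may still be missed, and the report should say so.

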4.2 Objectives and Endpoints (Group 2)

OBJECTIVES	ENDPOINTS
Primary Exploratory	
To explore perceptions of the QI strategies from the perspective of primary care clinicians.	No quantitative endpoint. Clinician perceptions will be assessed qualitatively.
Secondary Exploratory	
To explore aspects of effectiveness of the implementation strategies.	For randomized patients, initiation of either a PPI or discontinuation of all antiplatelet therapy based on chart review at week 3.
To explore the feasibility of delivering the patient activation tool	The proportion of patients randomized to receive the activation guide who were sent the guide in the prescribed period of time, as determined by chart review.

OBJECTIVES	ENDPOINTS
To explore the feasibility of delivering the clinician-level QI strategies	Proportion of patients whose clinician was sent the clinician-level strategy by the anticoagulation clinic staff in the prescribed time period per the clinic protocol. We will also separately calculate this endpoint for the two levels of the clinician QI strategy.
To explore process outcomes associated with the clinician notification + nurse facilitation implementation strategy	
For patients randomized to clinician notification + nurse facilitation:
 
Number of days taken for clinicians to send a response message to anticoagulation staff after first receiving the clinician notification.
 
Proportion of clinicians who documented their plan-of-care for the patient in the response message to the anticoagulation staff.
 
Proportion of patients randomized to clinician notification + nurse facilitation for whom the anticoagulation nurse provided patient education.
 
Proportion of patients randomized to clinician notification + nurse facilitation for whom the anticoagulation nurse pended the PPI order.

To explore the feasibility of prompting patient-clinician communication about medication optimization	
The number of days after delivery of the clinician-facing QI strategy at which the patient and the target clinician (or their healthcare team) had communication (either by phone, in person visit, or portal message) about medication optimization, based on chart review. This will be calculated overall and separately for each QI strategy.
 
For patients who had a communication with their clinician about medication optimization, the proportion in whom initial contact was made by the clinician vs. by the patient, according to chart review. This will be calculated overall and separately for each of the QI strategies.
 
For patients who contacted a clinician about medication optimization, the specialty of the clinician and whether the clinician who was sent the clinician notification was the target clinician. This will be determined separately based on chart review.
 
For patients who had communication with their clinician documented in the electronic health record, whether this occurred by phone, portal, or in-person/telehealth visit based on chart review.

OBJECTIVES	ENDPOINTS
To explore process measures associated with clinician notification	
For clinicians randomized to clinician notification:
 
Number of days taken for clinicians to send a response message to anticoagulation staff after first receiving the clinician QI strategy.
 
Proportion of clinicians who documented their plan-of-care for the patient in the response message to the anticoagulation staff.
 
The number of clinicians who appropriately documented changes in antiplatelet drugs or PPI in the EHR medication list.

To explore process outcomes associated with the clinician notification + nurse facilitation implementation strategy	
For patients randomized to clinician notification + nurse facilitation:
 
Number of days taken for clinicians to send a response message to anticoagulation staff after first receiving the clinician notification.
 
Proportion of clinicians who documented their plan-of-care for the patient in the response message to the anticoagulation staff.
 
Proportion of patients randomized to clinician notification + nurse facilitation for whom the anticoagulation nurse provided patient education.
 
Proportion of patients randomized to clinician notification + nurse facilitation for whom the anticoagulation nurse pended the PPI order.

To explore aspects of effectiveness of the implementation strategies.	
For randomized patients, initiation of either a PPI or discontinuation of all antiplatelet therapy at week 3 as determined by chart review.
 
Documentation of a recommendation by one of the patient's Michigan Medicine clinicians to discontinue antiplatelet therapy or initiate a PPI as indicated by a clinical documentation or by a change in the EHR medication list, ascertained by EHR review.

OBJECTIVES	ENDPOINTS
To explore the appropriateness of antiplatelet therapy used by patients at the time of study randomization.	The clinical appropriateness of antiplatelet therapy at the time of study initiation, classified as either (probably guideline concordant, probably not guideline concordant, or uncertain), based on detailed chart review and in reference to practice recommendations (Appendix 1).
To explore the appropriateness of medication changes in antiplatelet therapy during the trial.	For patients who either stopped antiplatelet therapy or initiated a PPI during the trial, to explore the appropriateness of antiplatelet management according to chart review at week 3. The clinical appropriateness of antiplatelet management will be determined according to pre-specified criteria (probably guideline concordant, probably not concordant, uncertain). See appendix 1 for criteria.

Additional objectives to be explored in qualitative interviews with clinicians:

- Acceptability of the implementation strategy components
- Barriers to successful implementation

Please see associated interview guide. The interview guide used to complete clinician assessments will be iteratively revised throughout the pilot study, allowing initial findings from assessments to inform subsequent assessments and ensuring capture of all relevant information necessary for effective planning of the future clinic-wide quality improvement trial.

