Verbal informed consent and semi-structured interviews with clinicians (research team) . This may occur as soon as week 5 if the clinician has already responded to messages for all of their patients involved in the trial.		X	X

Schedule of Anticoagulation Clinic Staff-Targeted Activities

Activity	Week 1-5	Week 6-8	Week 9-16
Anticoagulation clinic staff receive weekly list of up to 10 patients starting trial each week, and the name of the target clinicians (research team)	X		
Anticoagulation staff initiate clinician and patient facing QI strategies synchronously (anticoagulation clinic staff)	X		
Additional outreach, communication, or facilitation steps as per anticoagulation clinic protocol for clinician notification and clinician notification + nurse facilitation strategies (anticoagulation clinic staff)	X	X	
Verbal informed consent and semi-structured interviews with anticoagulation staff (research team)			X

1.4 Schedule of Activities – Group 2

A convenience sample of 8 primary care clinicians will be selected. Additionally, all eligible patients for whom the primary care clinician is the responsible provider on record for the anticoagulation clinic will be included in group 2. We anticipate that each included primary care clinician will have 1-2 eligible patient included in group 2, for a total of 8-16 patient participants.

For informational purposes, whether the research team performs the activity, or the anticoagulation clinic staff performs the activity is indicated in bold. Failure of the anticoagulation clinic staff to follow the clinical protocols for delivery of the patient and clinician level QI strategies will not be considered study deviations.

Schedule of Patient-Targeted Activities

Activity	Screening and randomization	Week 1	Week 2-4	Week 5-8	Week 9-12
Eligibility determination by chart review (research team)	X				

Activity	Screening and randomization	Week 1	Week 2-4	Week 5-8	Week 9-12
Randomization of patient to QI strategy (research team)	X				
Delivery of education and activation guide for patients randomized to receive it (anticoagulation staff)		X			
Possible outreach to the patient by their clinical care team and/or anticoagulation clinic staff as per usual clinical care (no research team activity)		X	X	X	
Chart review to ascertain exploratory outcomes (research team)			X	X	X

Schedule of Clinician-Targeted Activities

Activity	Screening, selection, and randomization	Week 1	Week 2-6
Eligibility determination (research team)	X		

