Selection of 8 primary care clinicians (research team)	X		
Randomization of selected clinicians to either clinician notification arm or clinician notification + nurse facilitation arm (research team)	X		
Delivery of clinician-facing QI strategies, synchronized with patient-level strategies (anticoagulation clinic staff)		X	

Additional outreach, communication, or facilitation steps as per anticoagulation clinic protocol for clinician notification and clinician notification + information relay strategies (anticoagulation clinic staff)			X
Verbal informed consent and semi-structured interviews with clinicians (research team). This may occur as soon as week 3 if the clinician has already responded to messages for all of their patients involved in the trial.			X

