8.3 Lost to Follow-Up

8.3.1 Group 1

If a patient is unable to be reached for assessment #1, #2, or #3, the data for the variables associated with that assessment will be coded as missing. If a patient is unable to be reached for assessment #1, no attempt will be made to reach them for assessment #2 or assessment #3. Even if patients are unable to be reached for assessment #1, #2, or #3, chart review will still be performed for that patient to evaluate the exploratory outcomes.

8.3.2 Group 2

Not applicable as no patient assessments will be conducted with group 2 participants. Chart review will be performed for patients in group 2 between study initiation and week 6.

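### Two Group 2 endpoints, medication change and its appropriateness, are read only at week 3, before the Week 2-6 outreach period ends, and the chart-review end date is contradictory

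*Combined protocol and SAP*

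**What the plan says.** Section 4.2 states the Group 2 medication-change endpoint twice. One row gives "initiation of either a PPI or discontinuation of all antiplatelet therapy based on chart review at week 3". A later row gives "initiation of either a PPI or discontinuation of all antiplatelet therapy at week 3 as determined by chart review". The appropriateness endpoint takes patients who stopped antiplatelet therapy or started a PPI while the trial was running, and is meant "to explore the appropriateness of antiplatelet management according to chart review at week 3". No other reading week is given for either endpoint.

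The Group 2 schedules in Section 1.4 set the surrounding calendar:

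- The clinician-facing strategy is delivered in Week 1.
- The Week 2-6 column of the clinician schedule contains "Additional outreach, communication, or facilitation steps as per anticoagulation clinic protocol for clinician notification and clinician notification + information relay strategies".
- In the patient schedule, chart review for exploratory outcomes is marked under Week 2-4, Week 5-8 and Week 9-12.

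Section 5.4.2 ends Group 2 participation after week 12. Section 8.3.2 gives a different chart-review window: "Chart review will be performed for patients in group 2 between study initiation and week 6".

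**The concern.** An outcome meant to show what the strategies led to should normally be read once they have had time to act. Here the only reading falls inside the period in which the clinic may still be contacting clinicians and patients. A patient whose antiplatelet drug is stopped or whose PPI is started in week 5 counts as unchanged.

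The appropriateness endpoint also has an internal mismatch. Its population is defined by changes over the whole trial, which lasts 12 weeks, but the judgement is tied to week 3. A patient who changes in week 5 belongs to that population, yet would be assessed on a status that predates the change.

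What is at stake is the descriptive picture of medication change among primary care patients, which is meant to inform the larger trial. The conflict over the chart-review window matters separately, because it decides whether data from weeks 7-12 exist at all.

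**Working it through.** The plan has no Group 2 figure to reproduce: Section 11.1.2 gives no sample-size calculation. The check compares dates.

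**Inputs**

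- Reading of both endpoints: week 3 (Section 4.2).
- Outreach and facilitation: weeks 2-6 (Section 1.4, Group 2 clinician schedule).
- Last chart review: week 12 (Section 1.4) or week 6 (Section 8.3.2).
- End of Group 2: after week 12 (Section 5.4.2).
- Group 2 size: 8-16 patients (Section 6.1.2).

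**Distance from the reading to each limit**

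- To the end of outreach and facilitation: 6 − 3 = 3 weeks.
- To the end of chart review under Section 8.3.2: 6 − 3 = 3 weeks.
- To the end of chart review under Section 1.4, and to the end of study: 12 − 3 = 9 weeks.

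So under either chart-review window, both endpoints are read before outreach ends and before chart review ends. By the end of week 3, weeks 2 and 3 of the five weeks 2-6 have passed: 2/5 = 40%. That is elapsed calendar time only.

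**Illustration of what could be missed**

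The documents give no rate of change. Assume, for illustration only, a constant weekly rate with a proportion p changed by week 12, and let p range from 20% to 60%. The proportion changed by week t is then F(t) = 1 − (1 − p)^(t/12).

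For p = 40%:

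- F(3) = 1 − 0.6^0.25 = 0.120
- F(6) = 1 − 0.6^0.5 = 0.225
- F(12) = 0.400
- F(3)/F(6) = 0.53 and F(3)/F(12) = 0.30

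Across p = 20% to 60%, week 3 captures 51-56% of the changes present at week 6 and 27-34% of those present at week 12.

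Expected numbers changed at p = 40%:

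| Patients | Week 3 | Week 6 | Week 12 |
|---|---|---|---|
| 8 | 1.0 | 1.8 | 3.2 |
| 16 | 1.9 | 3.6 | 6.4 |

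If changes cluster soon after the message is sent, week 3 captures more than this. If they wait on clinician replies, it captures less.

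**Which Group 2 endpoints are affected**

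Only the two named above. In Section 4.2, the endpoint on a documented clinician recommendation, which a medication-list change can also satisfy, has no week limit. Nor do the endpoints on clinician response time, nurse education, pended PPI orders and patient-clinician communication. Baseline appropriateness is judged at study initiation.

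**The case against.** The strongest reply is that little depends on week 3. Group 2 was added for a qualitative purpose, its quantitative endpoints are secondary exploratory, and the analysis is descriptive. Later changes are not wholly lost either, because the documented-recommendation endpoint is open-ended. Both points stand and keep the matter minor. They do not remove it: that endpoint can be met by a recommendation alone, and it carries no judgement of appropriateness.

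A second reply is that a schedule column shows when an activity may occur, not how long it lasts. That also stands. The 40% should not be read as the share of the effect captured, and the illustration depends on its assumed rate.

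Four stronger readings may tempt a reader, and the documents support none of them:

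- **Week 3 penalises the nurse-facilitation arm most.** The Week 2-6 row covers both clinician strategies. Nurse facilitation waits for a clinician decision, which could delay changes, but it is also meant to ease that decision and has the nurse prepare orders, which could bring changes forward. The direction of any between-arm bias is unknown.
- **A week-5 reading would make Group 2 comparable with Group 1.** Group 1's week-5 reading comes from patient interview and Group 2's from chart review. Group 1 clinicians are drawn at random, while Group 2 clinicians are a convenience sample. No comparison between the groups is planned.
- **Strategy delivery continues to week 8.** The patient outreach marked in Week 5-8 is labelled as usual clinical care.
- **Chart review to week 12 is already settled.** That holds only if Section 1.4 prevails over Section 8.3.2.

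**Conclusion.** The point holds, as a minor one. The Group 2 medication-change endpoint and the appropriateness-of-change endpoint are read only at week 3. That is 3 weeks before the scheduled outreach and facilitation period ends and 9 weeks before Group 2 ends. Changes in between are missed by these two endpoints, and the appropriateness endpoint does not fit its own population. Sections 1.4 and 8.3.2 contradict each other on when chart review stops.

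The size of the loss cannot be established from the documents. The 51-56% and 27-34% figures are conditional on an assumed constant rate. The date comparison assumes that the Week 2-6 column counts from each patient's entry or from the last patient in the clinician's cluster. The schedule does not say which, but on either count it ends no earlier than a patient's own week 6.

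**What to change.** 1. Reconcile Sections 1.4 and 8.3.2 so that one end date governs Group 2 chart review.
2. In Section 4.2, keep week 3 as an early reading and add a reading of both endpoints at the end of the reconciled window. That is week 12 if Sections 1.4 and 5.4.2 govern. It should be no earlier than week 6, which still covers the whole scheduled outreach period.
3. Tie the appropriateness endpoint's population to the same reading, so that each change is judged on a status recorded after it.
4. State how patients who stop warfarin or leave the service before the later reading are counted. Section 8.1.2 deals only with the first 3-5 weeks.

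The cost is wording if Section 1.4 already governs. If Section 8.3.2 governs, a week-12 reading adds modest chart abstraction in 8-16 patients. Neither case adds patient contact.
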